Change in study sponsorship and to bring into line with Novartis processes.

LIST OF ABBREVIATIONS

Text changed:

CRO Clinical Research Organization
GCPH Global Clinical Program Head
HA Health Authority

Reason for change:

Change in study sponsorship and to bring into line with Novartis processes.

Section: 7.4.10.2. Pregnancy Reporting

Text changed:

To ensure subject safety, each pregnancy must be reported to the sponsor within **24 hours** of learning of its occurrence.

Reason for change:

Change in study sponsorship and to bring into line with Novartis processes.

Section: 7.4.10.4. Action to be taken if pregnancy occurs in a female partner of a male study subject

Text changed:

The investigator will record pregnancy information on the appropriate form and submit it to the sponsor within **24 hours** of learning of the partner's pregnancy.

Reason for change:

Change in study sponsorship and to bring into line with Novartis processes.

Section: 11.7. Time Period and Frequency of Detecting AEs and SAEs

Text changed:

Reason for change:

Change in study sponsorship and to bring into line with Novartis processes.

Section: 11.13. Regulatory Reporting Requirements for SAEs

Text changed:

An investigator who receives an investigator safety report describing a SAE(s) or other specific safety information (e.g., summary or listing of SAEs) from the sponsor will file it with the IB and will notify the - **IRB/IEC**, if appropriate according to local requirements.

Reason for change:

Change in study sponsorship and to bring into line with Novartis processes.

Section: 17. DATA MANAGEMENT

Text changed:

Adverse events (AEs) and concomitant medications terms will be coded using Medical Dictionary for Regulatory Activities (MedDRA) and **a custom drug dictionary** -.

-Reason for change:

Change in study sponsorship and to bring into line with Novartis processes.

Section: 19.4. Quality Control (Study Monitoring)

Text changed:

In accordance with applicable regulations, GCP, and **Novartis**- procedures, **Novartis personnel (or designated Clinical Research Organization [CRO]) will contact** the site prior to the start of the study to review with the site staff the protocol, study requirements, and their responsibilities to satisfy regulatory, ethical, and the sponsor's requirements.

Reason for change:

Change in study sponsorship and to bring into line with Novartis processes.

Section: 19.6. Study and Site Closure

Text changed:

Upon completion or termination of the study, **Novartis personnel (or designated CRO)** will conduct site closure activities with the investigator or site staff (as appropriate), in accordance with applicable regulations, ICH GCP, and **Novartis**- Standard Operating Procedures.

Reason for change:

Change in study sponsorship and to bring into line with Novartis processes.

Section: 19.7. Records Retention

Text changed:

Essential documents (written and electronic) should be retained for a period of not less than fifteen (15) years from the completion of the Clinical Trial unless the Sponsor provides written permission to dispose of them or, requires their retention for an additional period of time because of applicable laws, regulations and/or guidelines.

-Reason for change:

Change in study sponsorship and to bring into line with Novartis processes.

Section: 19.8. Provision of Study Results to Investigators, Posting of Information on Publicly Available Clinical Trials Registers and Publication

Text changed:

Novartis aims to post a results summary to the Novartis Clinical Trial Results website (www.novartisclinicaltrials.com) and other publicly available registers no later than twelve (12) months after the last subject's last visit (LSLV). In addition, upon study completion and finalization of study report, Novartis aims to submit results of the study for publication.

-When - publication - is not feasible, please refer to the Novartis Clinical Trial Results website (www.novartisclinicaltrials.com) for a summary of the trial - results -.

4.4.1	Demography (ADSL).....	28
4.4.2	Initial diagnosis of primary tumor type under study	29
4.4.3	Adverse events (ADAE)	29
4.4.4	Surgery and radiotherapy	30
4.4.5	Concomitant medication and blood and blood supportive care products	30
4.4.6	Time to event (Duration of response and Progression-free survival) and best confirmed overall response	31
4.4.7	Imputation of missing exposure end dates	32
4.5	Multiple Assessments	33
4.6	Laboratory parameters derivations	33
4.7	ECG parameters.....	33
4.8	Cardiac Scan Modalities (ECHO)	34
4.9	Left ventricular ejection fraction	34
4.10	Vital signs	34
4.11	Statistical models.....	35
5	Reference.....	35

List of abbreviations

AE	Adverse Event
ASI	Adenocarcinoma of the small intestine
ATC	Anaplastic Thyroid Cancer
BTC	Biliary Tract Cancer
CRF	Case Report Form
CSR	Clinical Study Report
DMS	Document Management System
ECG	Electrocardiogram
eCRF	electronic Case Report Form
eCRS	electronic Case Retrieval Sheet
[REDACTED]	[REDACTED]
GIST	Gastrointestinal stromal tumor
HCL	Hairy Cell Leukemia
HGG	High Grade Glioma
[REDACTED]	[REDACTED]
IA	Interim Analyses
LGG	Low Grade Glioma
MedDRA	Medical Dictionary for Regulatory Activities
MM	Multiple Myeloma
MRD	Minimal Residual Disease
NGGCT	Non-geminomatous germ cell tumor
NSGCT	Non-seminomatous germ cell tumor
PK	Pharmacokinetics
PRO	Patient-reported Outcomes
RAP	Reporting & Analysis Process
SAP	Statistical Analysis Plan
SAS	Statistical Analysis System
TFLs	Tables, Figures, Listings
WHO	World Health Organization

1 Introduction

This statistical analysis plan (SAP) details all planned analyses to support the final clinical study report (CSR) and publication of final study results from BRF117019/CDRB436X2201. This is a phase II study to evaluate the clinical efficacy and safety of the combination therapy of dabrafenib (DRB436) and trametinib (TMT212) using a single-arm multi-histology study design in several rare cancer types.

In this SAP, references will be made to the following documents:

- Protocol amendment 11 dated 04 Jun 2020
- Annotated electronic Case Report Form (eCRF) BRF117019/CDRB436X2201 SV16.0
- Charter for the Independent Data Monitoring Committee (IDMC) version 2.0 dated 23 Jun 2016

1.1 Study design

This is a Phase II, open-label, non-randomized, multi-center study of oral dabrafenib in combination with oral trametinib in subjects with rare cancers with the BRAF V600E mutation. The following histologies will be included in this study: ATC, BTC, GIST, WHO Grade 1 or 2 glioma, WHO Grade 3 or 4 glioma, NSGCT/NGGCT, ASI, HCL and MM (Cohorts 1 to 9, respectively).

For each cohort, up to 25 evaluable subjects will be enrolled in the primary analysis cohort. If a given cohort is stopped early for efficacy, a histology specific expansion cohort may be opened to allow for additional patient enrollment.

The primary analysis cohort is comprised of those patients enrolled within a histology-specific group prior to capping at 25 patients per cohort or prior to early stopping for efficacy or futility. The primary analysis cohort will form the basis of the Bayesian modelling of ORR.

If a cohort closes early at an interim analysis because it meets the rules for early stopping for efficacy, an expansion cohort may be opened to allow additional patient enrollment for that particular histology. The patients in the expansion cohort will provide supportive efficacy data and will NOT contribute to the Bayesian modeling of ORR. The expansion cohort(s) will enroll subjects for the duration of trial enrollment.

Only subjects with histologically or cytologically confirmed advanced disease with no available treatment options as determined by locally or regionally available standards of care and by the treating physician's discretion will be eligible for enrollment. Subjects may be enrolled based on local testing of the BRAF V600E mutation and mutation status will be confirmed by a central reference laboratory.

Subjects will receive dabrafenib 150 mg BID orally plus trametinib 2 mg once daily orally on a continuous dosing schedule. An adaptive design with multiple interim evaluations will determine if one or more histologic cohorts should discontinue enrolment early due to either success or futility. Evaluations are based on a hierarchical statistical model that borrows information in a limited way from histologies that demonstrate similar response rates based on the accumulated trial data. A complete description of the study design and rationale is included in the Protocol.

1.2 Study objectives and endpoints

The study objectives and corresponding endpoints are presented in [Table 1-1](#).

Table 1-1 Study Objectives and Endpoints

OBJECTIVES	ENDPOINTS
Primary	

 To determine the ORR of dabrafenib and trametinib anti-cancer combination therapy in subjects with selected rare BRAF V600E mutated solid tumors or hematologic malignancies. 	
 Tumor response as defined by: RECIST, v1.1 for solid tumor histologies, Modified RANO and RANO for glioma or established response criteria for specific hematologic malignancies
Secondary	

 To determine the duration of response of dabrafenib in combination with trametinib in subjects with selected rare BRAF-mutated cancers 	
 Duration of response

 To determine PFS of dabrafenib in combination with trametinib in subjects with selected rare BRAF-mutated cancers 	
 Investigator-assessed PFS

 To determine OS of dabrafenib in combination with trametinib in subjects with selected rare BRAF-mutated cancers 	
 OS

 To determine the safety of dabrafenib in combination with trametinib in subjects with selected rare BRAF-mutated tumors 	
 Change from baseline in physical examination findings, vital signs, AEs, laboratory values and cardiac assessments

Abbreviations: AE, adverse events; [REDACTED]

[REDACTED] ORR, overall response rate; OS, overall survival; [REDACTED] PFS, progression-free survival; [REDACTED] PK, pharmacokinetics; RANO, Response Assessment for Neuro-Oncology; RECIST, Response Evaluation Criteria in Solid Tumors; [REDACTED]

2 Statistical methods

2.1 Data analysis general information

Analysis datasets and outputs will be produced in the GPSII system using SAS version 9.4 (or later).

Data from all participating centers will be pooled prior to analysis. Subject accrual is spread thinly across centers and summaries of data by center would be unlikely to be informative and therefore will not be provided.

All data up to death or study withdrawal will be included in each analysis. Unscheduled visits will not be included in summaries, except to derive minimum/maximum post-baseline or on-treatment values. Unscheduled visits will be presented in subject listings.

Planned times relative to study drug dosing will be used in all tables and summary figures.

Unless otherwise stated, continuous variables will be summarized with n, mean, median, standard deviation, minimum and maximum, and categorical variables will be summarized with frequency counts and percentages.

2.1.1 General definitions

Study treatment

Study treatment in this study refers to either dabrafenib or trametinib.

Reference dates

There are two reference dates:

- The date of screening is the reference date for determination of age, since age is an eligibility requirement.
- The study treatment start date is the reference date for efficacy and safety.

Study day

If the date of interest occurs on or after the reference date then the study day will be calculated as (date of interest - reference date) + 1. If the date of interest occurs before the reference date then the study day will be calculated as (date of interest - reference date). There is no study day 0.

Duration and elapsed time

Durations (e.g., the duration of an adverse event, duration of exposure, etc.) are calculated as the stop date minus the start date plus one.

For elapsed time (e.g., the time since initial diagnosis):

- If the event date is on or after the reference date, then the elapsed time is the event date minus the reference date + 1
- If the event date is before the reference date then the elapsed time is the event date minus the reference date

When reporting time to event (TTE) durations such as PFS in months, divide the number of days by 30.4375; to report in weeks divide the number of days by 7; to report in years divide the number of days by 365.25.

Baseline

Baseline will be defined as the most recent, non-missing value prior to or on the first study treatment dose date. For laboratory data, baseline will be defined as the most recent, non-missing value from a central laboratory prior to or on the first study treatment dose date. If there are no central labs collected for a subject and lab test prior to or on the first dose of study treatment, the most recent, non-missing value from a local laboratory prior to or on the first dose of study treatment will be defined as the baseline value.

Change from baseline

Change from baseline will be presented for safety data. Change from baseline is calculated as: For records occurring after baseline: (visit value) - baseline value.

Percent change from baseline is calculated as:

For records occurring after baseline: ((change from baseline) / Baseline value) *100.

If either the baseline or visit value is missing, the change from baseline and/or percent change from baseline is set to missing as well.

Time in relation to treatment

Adverse events, serious adverse events, death, laboratory data, vitals, ECG and ECHO, will be assigned to the study time periods defined below. Partial dates will be imputed into full dates, if applicable, for slotting data to the appropriate categories below (see Section 4.4). Flag variables (time in relation to study treatment) indicating the study time periods will be added to these datasets.

Pre-therapy is defined as the time prior to the subject's first dose of study treatment.

On-therapy is defined as the time from first dose of study treatment until 30 days after the last dose date of study treatment.

Post-therapy is defined as any time beyond the on-therapy period.

Some datasets include the first dose day as On-therapy and some exclude the first dose date as On-Therapy. The first dose day (Day 1) is considered pre-therapy for ECOG, ECG, vital signs, liver events, lab tests, and cardiac scan. The first dose day (Day 1) is considered to be On-therapy for adverse events and concomitant medications.

Study time period for concomitant medications and blood and blood supportive care products

Concomitant Medication and Blood and Blood Supportive Care Product start and end dates will be assigned to study time periods in relation to first dose of study treatment as defined below. The start date reference time flag variables and end date reference time flag variables will be added to the concomitant medications and blood and blood supportive products datasets, respectively.

Start relative to treatment: Assign to 'BEFORE' if start date is prior to study treatment start date or if subject has not taken any study treatment or (start date is missing and end date is before study treatment start date). Else assign to 'DURING' if the start date falls on or between the first and last dose dates of study treatment or if subject is ongoing (not all study treatment

discontinuation records completed) or start date is missing. Else assign to 'AFTER' if start date is after the on-therapy period.

End relative to treatment: Assign to 'BEFORE' if end date is prior to study treatment start date or if subject has not taken any study treatment. Else assign to 'DURING' if end date falls on or between the first and last dose dates of study treatment or if subject is ongoing (not all study treatment discontinuation records completed) or (end date is missing and start relative to treatment not 'AFTER'). Else assign to 'AFTER' if start date is after the on-therapy period or (end date is missing and start relative to treatment='AFTER').

Only on-therapy blood and blood supportive care products that start after the start of study treatment are included in the Blood Products and Blood Supportive Care Product summaries. Therefore, for summary tables, include blood and blood supportive care product records where start relative to treatment in ('DURING') and end relative to treatment in ('DURING','AFTER'). All data will be reported in listings.

Concomitant medication start relative to treatment and end relative to treatment flags are used to select data to include in the Concomitant Medication summaries as follows:

- **Summary of Concomitant Medications:** This summary will contain medications including those with start date prior to study treatment start date and continue (missing end date or end date after study treatment start date) on therapy. Note that any medications with start date and end date prior to study treatment start date will be excluded. In addition, any medication that was started during post-therapy will be excluded. Include concomitant medication records where start relative to treatment in ('BEFORE','DURING') and end relative to treatment in ('DURING','AFTER').
- **Summary of Concomitant Medications with On-Therapy Onset:** This summary will contain medications with start date after study treatment start date. In addition, any medication that was started during post-therapy (see above for definition of post-therapy) will be excluded. Include concomitant medication records where start relative to treatment in ('DURING') and end relative to treatment in ('DURING','AFTER').

Other derivations or data handling procedures related to this analysis plan are given in section 4.

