45. **PK Sampling - Week 8, Week 12, and Follow-up Visit:** A single 2 mL blood sample for PK analysis of trametinib, dabrafenib and its metabolites (hydroxy-dabrafenib and desmethyl-dabrafenib) will be collected at Week 8 (pre-dose), Week 12 (pre-dose), and at the Follow-up Visit. Subjects with morning clinic visits are to be instructed to withhold their morning doses of study treatment and PK samples will be collected prior to dabrafenib administration. Subjects with afternoon clinic visits are to be instructed to take their morning doses as usual and PK samples will be collected 4 to 8 hrs following dabrafenib administration. **Samples at the Follow-up Visit are no longer requested for collection as of Protocol Amendment 11.**

[REDACTED]

- 
54. **STUDY TREATMENT:** Subjects must receive their supply of study treatments within 3 days of enrollment.
55. **FOLLOW-UP VISIT:** The Follow-up Visit should take place within 28 days (+7 days) of the last dose of study treatments. If the subject is unable to return to clinic, site staff is encouraged to call subject for assessment of AEs.
56. **FOLLOW-UP VISIT:** All safety and laboratory assessments should be performed unless the assessments were performed within 4 weeks prior to the Follow-up Visit.
57. **FOLLOW-UP VISIT:** If the last cardiac assessment was >12 weeks prior to the Follow-up Visit, an ECHO should be performed.
58. **EXTENDED FOLLOW-UP:** The following evaluations will be performed for all patients in all cohorts.
- a) Dermatologic exam. Exams will be performed every 4 weeks (+/-7 days) for the first 6 months. The skin will be carefully examined and pictures and biopsy will be taken of any new or changed skin lesions.
 - b) If study treatments are permanently discontinued prior to the subject having confirmed disease progression, the subject will continue to have disease assessments every 12 weeks (+/-14 days) until disease progression or initiation of new anti-cancer treatment, or death, whichever comes first.
 - c) Subjects will be followed every 12 weeks (+/-14 days) for survival until the subject dies or withdraws consent or is lost to follow up, or up to a time period as defined in Section 16.3. Survival follow up may be performed via clinic visit, a telephone contact, an email or by mail. The initiation of any new anti-cancer treatment(s) and date of last contact should also be documented.

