18.3.3.1.2 Clinical Laboratory Evaluations

Hematology and clinical chemistry data will be summarized by each scheduled assessment according to CTCAE, version 4.0, grade. The proportion of values lying outside the reference range will also be presented for laboratory tests that are not graded because there are no associated CTCAE grading criteria. Summaries will include data from scheduled assessments only, and all data will be reported according to the nominal visit date for which it was recorded (i.e., no visit windows will be applied). Unscheduled data will be included in “overall” and “any post-screening” summaries which will capture a worst case across all scheduled and unscheduled visits post first dose of study treatment.

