2.7.3 Laboratory data

The full list of laboratory tests is given in the study protocol section 7.4.8.

Laboratory grades will be reported using the Common Terminology Criteria for Adverse Events (CTCAE v4.0).

Summaries of worst case grade increase from baseline grade will be provided for all the lab tests that are gradable by CTCAE v4.0. These summaries will display the number and percentage of subjects with a maximum on-therapy grade increasing from their baseline grade. Any increase in grade from baseline will be summarized along with any increase to a maximum grade of 3 and any increase to a maximum grade of 4. Missing baseline grade will be assumed as grade 0. In addition, the summary will include grade increase from baseline by scheduled

visits. For laboratory tests that are graded for both low and high values, summaries will be done separately and labeled by direction, e.g., sodium will be summarized as hyponatremia and hypernatremia.

For lab tests that are not gradable by CTCAE v4.0, summaries of worst case changes from baseline with respect to normal range will be generated. Decreases to low, changes to normal or no changes from baseline, and increases to high will be summarized at each scheduled visit as well as for the worst case on-therapy. If a subject has a decrease to low and an increase to high during the same time interval, then the subject is counted in both the “Decrease to Low” categories and the “Increase to High” categories. Detailed derivation of baseline assessment is specified in Section 2.1.1.

Unless otherwise specified, the denominator in percentage calculation at each scheduled visit will be based on the number of subjects with non-missing value at each particular visit.

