An eDISH plot showing the peak on-therapy total bilirubin versus peak on-therapy ALT will be plotted by histological cohort combining primary analysis and expansion cohorts. Upon data review during the conduct of the study, an additional eDISH plot might be considered showing peak on-therapy total bilirubin versus peak on-therapy AST if there are potential cases based on AST rather than ALT. Subject plots showing the time course of ALT, AST, ALP and total bilirubin will also be produced. The number and percentage of subjects with ALT, AST and bilirubin above relevant thresholds (e.g. 3 x ULN) at any time on-therapy will be displayed. Criteria relating to the combined elevations of ALT or AST and bilirubin are based on the peak values at any time on-therapy and do not have to be concurrent.

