2.12 Interim analysis

Interim analyses have been carried out to monitor efficacy and safety at regular intervals through the study enrollment and for health authority submission and publication after the end of enrollment. Details of interim analyses are given in section 18.3.2 of the protocol and the interim reporting and analysis plans.

3 Change to protocol specified analyses

No changes were made to analyses specified in the protocol.

4 Appendix

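### The SAP cuts the worst-case laboratory and liver displays at 30 days after last dose, where the protocol sets no end date and allows the Follow-up Visit to day 35, and does not declare the change

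*SAP*

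**What the plan says.** **Time window.** SAP 2.1.1 assigns laboratory data, among other data, to study periods. "On-therapy is defined as the time from first dose of study treatment until 30 days after the last dose date of study treatment". Beyond that, "Post-therapy is defined as any time beyond the on-therapy period".

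**Displays that use it.** SAP 2.7.3 reports "the number and percentage of subjects with a maximum on-therapy grade increasing from their baseline grade". Tests that CTCAE does not grade get a worst-case on-therapy shift against the normal range. The eDISH plot uses peak on-therapy bilirubin and ALT. The liver table counts subjects with values "above relevant thresholds (e.g. 3 x ULN) at any time on-therapy will be displayed", and the combined ALT or AST and bilirubin criteria also use on-therapy peaks. SAP 4.5 admits unscheduled data only to worst-case on-therapy displays.

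**Protocol schedule.** Footnote 55 to the Time and Event Table (Protocol 7.1): "The Follow-up Visit should take place within 28 days (+7 days) of the last dose of study treatments". Footnote 56: "All safety and laboratory assessments should be performed unless the assessments were performed within 4 weeks prior to the Follow-up Visit".

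**Protocol analysis.** Protocol 18.3.3.1.2 places unscheduled laboratory data in overall summaries "which will capture a worst case across all scheduled and unscheduled visits post first dose of study treatment".

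**Declared changes.** SAP section 3: "No changes were made to analyses specified in the protocol".

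**The concern.** The 30-day cut falls inside the permitted window of a visit at which chemistry and hematology are required. Two patients with the same abnormality at the end-of-treatment visit, one seen on day 30 and one on day 33, are handled differently: the first enters the worst-case table and the eDISH plot, the second does not. Both would count under the protocol's rule.

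At stake is the completeness of the displays that a safety reader looks at first: the maximum-grade shift table and the combined liver-elevation display. The SAP also tells that reader that nothing was changed, so there is no prompt to look elsewhere.

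**Working it through.** The plan states no figure to reproduce. The check is date arithmetic and a comparison of rules.

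**1. Size of the gap.**
- Latest in-window Follow-up Visit: 28 + 7 = day 35 after last dose (Protocol 7.1, footnote 55).
- End of on-therapy: day 30 (SAP 2.1.1).
- Uncovered days: 35 − 30 = 5, namely days 31 to 35.

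**2. Does the 4-week waiver close it?** Under footnote 56, a visit on day *v* can skip the draw only if one was taken on or after day *v* − 28.
- Visit on day 31: needs a draw on or after day 31 − 28 = 3.
- Visit on day 35: needs a draw on or after day 35 − 28 = 7.

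A patient whose last draw was on the day of last dose gets no waiver at these visits, so the gap stays open.

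**3. Does early drawing close it?** Protocol 7.4.8 allows laboratory tests up to 7 days before the scheduled visit. For a visit on day 35, the draw may be taken from day 35 − 7 = 28. This permits a draw by day 30 but does not require one. It can reduce the loss, not remove it.

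**4. Share of follow-up draws affected.** The documents give no distribution of visit timing, so the range below rests on assumptions:

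| Assumed timing of the draw | Share on days 31–35 |
|---|---|
| All by day 30 | 0% |
| Even over days 1–35 | 5/35 = 14% |
| Even over days 28–35 | 5/8 = 62.5% |
| Even over days 29–35 | 5/7 = 71% |

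These are shares of draws. They are not shares of subjects with a new worst grade or a liver signal, which cannot be derived.

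**5. Values after day 35.** Protocol 7.4.8 requires significantly abnormal results to be repeated until they return to normal or baseline. Protocol 7.4.8 and 16.6 require Grade 3 or 4 laboratory abnormalities at withdrawal to be followed to Grade 2 or less, unless improvement is unlikely because of the underlying disease. Protocol 8.1.3.1.3 requires liver chemistries to be monitored after a stopping event until they resolve, stabilise or return to baseline. Any worsening in these repeats after day 30 counts under Protocol 18.3.3.1.2 but not under SAP 2.7.3.

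**6. Direction.** A maximum over a subset of values cannot exceed the maximum over all of them. The cut can lower or leave unchanged the number of subjects with a worst-case abnormality; it cannot raise it.

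**7. Consistency within the SAP.** The ECG worst case (SAP 2.7.4.1) and the vital-sign worst case (SAP 2.7.4.2) are post-baseline, with no 30-day limit. SAP 2.1 says that data up to death or study withdrawal enter each analysis. The laboratory and liver worst cases depart from both.

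**The case against.** **The values remain visible elsewhere.** SAP 2.7.3 also gives grade increases and normal-range shifts by scheduled visit, and subject plots of liver chemistry over time. SAP 4.6 flags out-of-range values in listings. None of these has a stated 30-day cut. This stands and limits the point to the worst-case, eDISH and threshold displays. A reader might infer that Follow-up Visit laboratory data as a class are lost from the report; the documents do not support that, since draws by day 30 stay in everywhere.

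**Serious liver events have another route.** Protocol 11.2 makes combined ALT and bilirubin elevation a protocol-specific SAE. Protocol 11.7 records related SAEs up to any follow-up contact and allows related AEs to be reported after 30 days. The special-interest summary in SAP 2.7.1.1 includes hepatic disorders with no stated on-therapy limit. A reader might infer that a late liver signal would go unreported; that goes too far. This route does not cover every graded abnormality, though, and does not populate the eDISH plot.

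**A 30-day window is conventional, and detail was delegated.** It matches the AE collection period in Protocol 11.7, and Protocol 18.3.3.1 leaves full safety detail to the analysis plan. This explains the choice. But 18.3.3.1.2 is itself specific about the laboratory worst case, so narrowing it is a change to declare.

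**Any fixed cut makes inclusion depend on date.** True, which is a reason to follow the protocol's open-ended rule. Extending the cut to day 35 would cover the visit but still truncate that rule and lose later repeats.

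**Conclusion.** The discrepancy is real and narrow. The SAP's worst-case laboratory, eDISH and liver-threshold displays stop at day 30. The protocol's laboratory worst case has no end date, and its Follow-up Visit runs to day 35. Section 3 of the SAP is inaccurate on this point.

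The loss covers follow-up draws on days 31 to 35 and later repeats. Its size is unknown: 0% to 71% of follow-up draws under the timings assumed above, possibly lower where draws are taken ahead of the visit. A reader might take one of the higher percentages as an estimate of missed abnormalities; the documents give neither visit timing nor the number of abnormalities first seen after day 30, so no such estimate is available.

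The effect is one-sided, towards fewer reported abnormalities. It concerns descriptive safety displays only and does not touch efficacy results or error rates.

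**What to change.** Either of two changes would do:

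- **Preferred:** in SAP 2.7.3, define the laboratory and liver worst case (grade shifts, normal-range shifts, eDISH, threshold counts and combined criteria) over any value after first dose, scheduled or unscheduled. This matches Protocol 18.3.3.1.2 and the post-baseline approach the SAP already uses for ECG and vital signs. SAP 4.5 needs matching wording so that unscheduled values enter these displays.
- **Alternative:** keep the 30-day on-therapy displays, add a post-baseline worst-case column and liver display beside them, and record the 30-day cut in SAP section 3 as a change from the protocol, with its reason.

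The 30-day window can stay for AEs, where it matches the collection period.

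The cost is a small derivation change with no new data. Abnormality rates may rise slightly, and some late values may reflect subsequent therapy. That risk lies mainly with the later repeats, because Protocol 16.3 asks for the Follow-up Visit to be completed before any new anti-cancer treatment starts. Showing the two windows side by side would let a reader judge this.
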